8.2.3. Expected Adverse Events

Adverse events described in the Investigator's Brochure or that have occurred previously in the course of the active studies for this product (unless the frequency/severity or consequences have changed) are considered expected adverse events.

8.2.4. Intensity or Severity of Adverse Events

Assignment of the grade of severity of adverse events will be based on intensity of symptoms, degree of limitation of usual daily activities, or level of abnormality of objective clinical signs or laboratory parameters. Adverse events will be graded according to their severity using the following criteria:

Mild: the adverse event is transient or minimal and either resolves spontaneously or no treatment is required. Symptoms do not interfere with subject's daily activities.

Moderate: the adverse event required only brief treatment with prescription medication and/or intervention but produced no sequelae and required no hospitalization; symptoms may interfere with daily activities; symptomatic, moderate change in activity; no change in social activities.

Severe: the event produced sequelae that required prolonged treatment with prescription medication, intervention and/or hospitalization; interrupts subject's usual daily activities; incapacitating, requires bed rest, absence from work and/or a decrease in social activities.

8.2.5. Relatedness of Adverse Event to an Intervention

An adverse event can be assessed as:

- a. Likely Related - The adverse event is likely to be related to the study product(s)
- b. Possibly Related - The adverse event may be related to the study product(s)
- c. Likely Unrelated - The adverse event is unlikely to be related to the study product(s)

If an adverse event is evaluated as not related to the study product, there must be an alternative etiology in the Investigator's assessment for that event documented in the subject's medical records.

9. EVALUATIONS AND STATISTICAL METHODS

9.1. Evaluations

The following evaluations relating to tolerability, safety and clinical benefit will be made:

1. Adverse events (AEs) suspected to be related to injections of HGF plasmid
2. Discontinuations related to adverse effects from the injections of HGF plasmid
3. All AEs up to Month 3, Month 6, Month 12, and Month 18
4. Serious adverse events (SAEs) up to Month 3, Month 6, Month 12, and Month 18
5. Number of deaths and cause over the 18 month period up to Month 3, Month 6, Month 12, and Month 18
6. Number of subjects in whom the largest ulcer healed completely or gets smaller (photo confirmation) at 6, 12 and 18 months (cumulative)
7. Number of subjects in whom rest pain (based on the 100 mm VAS scale) reduces by 20 mm or more or was completely relieved at 6, 12 and 18 months (cumulative)
8. Change in VascuQol Questionnaire (QOL) score compared to the baseline at 6, 12 and 18 months
9. Number of subjects revascularized (bypass or endovascular intervention) up to Month 3, Month 6, Month 12, and Month 18
10. Number of subjects with minor and number of subjects with major amputations (at or above the ankle) up to Month 3, Month 6, Month 12, and Month 18

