Prior to dosing on Day 0, ulcer photography and tracing of the largest ulcer as at Screening (with ulcer debridement occurring prior to photography and tracing) will be completed again for establishing stability of the largest ulcer and of additional ulcers on the index leg prior to randomization. Ulcer photographs and photographs of the index leg will be taken at each visit (Day 14 through Month 18) and prior to any planned intervention of the index leg (surgical revascularization or major amputation). If the largest ulcer on the index leg heals during the study period, the ulcer must be re-evaluated 2 weeks after healing to confirm it has remained healed for a period of 2 weeks (this will require an additional visit to the site). Ulcer healing will be confirmed later via photographs by the study entry committee. *Ulcer and leg photographs must continue to be taken throughout the study period, regardless of the healing of the largest ulcer.*

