4.11. Ischemic Rest Pain Measurement

The severity of rest pain based on the average over the previous 7 days will be recorded using the 10 cm visual analog scale (VAS) (see Appendix E). The VAS score must be documented at all visits and prior to any planned intervention (revascularization or major amputation). In order to assess rest pain adequately, the use of pain medication/opioids must be specifically documented in the CRF during the VAS evaluation period. The subject should not be allowed to see his previous rest pain measurements nor should the score be revealed to him/her.

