2.5.5 Efficacy Analysis

- Ulcer improvement**

A table showing the number of subjects completely healed in the target ulcer will be provided at up to 6 months, > 6 months to 12 months, from >12 months to 18 months. If available, the number of subjects with at least 20% reduction in bi-dimensional size (by measuring largest diameters) will be provided. The reduction in bi-dimensional size will be calculated by taking the product of the largest diameters for each baseline and postbaseline measurement, then subtracting the baseline result from the postbaseline result.

- Ischemic Rest pain (of the index leg) using a 10 cm VAS scale**

Rest pain severity will be assessed at the specified predetermined time points. Rest pain severity will also be assessed prior to surgical revascularization or major amputation (of the index leg). A table showing the number of subjects reduced by ≥ 20 mm from baseline in VAS score will be provided at up to 6 months, > 6 months to 12 months, from >12 months to 18 months. Summary statistics will be provided for baseline and change from baseline for each visit and LOCF. One sample t-test for change-from-baseline will be performed. If death occurs, the worst score prior to death instead of last observation will be carried forward.

- Hemodynamic Measurements**

Summary statistics will be provided for baseline and change from baseline for hemodynamic parameters (right/left brachial systolic pressure, ankle systolic pressure measured at dorsalis pedis and posterior tibial, toe systolic pressure, calculated ABI, and calculated TBI) by visit. At each visit, only subjects who have a non-missing value at both baseline and the specific visit will be summarized. Two-sided one-sample t-test will be performed for each visit and LOCF.

- Subjects with any worsening CLI event of index leg**

A summary table and listing of worsening CLI-related events of the index leg including any new or worsening events, worsening rest pain, new ulcer or worsening ulcer, new or worsening wound infection, peripheral vascular intervention, complication of a peripheral vascular intervention, cellulitis, and amputation due to worsening CLI will be provided.

- Subjects who either died, had MI, Stroke, revascularization (by surgical bypass, by endovascular intervention, by hybrid procedure), major amputation, or all-cause death**

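### The protocol's ulcer benefit count accepts any shrinkage, cumulatively and without a control arm, so if ulcers are stable on average chance alone marks 50%, 67% and 75% as improved by Months 6, 12 and 18; the SAP cures this only in part

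*Protocol*

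**What the plan says.** Protocol 9.1 lists evaluations of tolerability, safety and clinical benefit. Item 6 is the ulcer count: "Number of subjects in whom the largest ulcer healed completely or gets smaller (photo confirmation) at 6, 12 and 18 months (cumulative". Item 7 counts subjects whose rest pain "reduces by 20 mm or more or was completely relieved at 6, 12 and 18 months (cumulative". Complete healing must be rechecked after two weeks (Protocol 4.9 and 5.18), but no recheck is stated for an ulcer that is merely smaller.

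On how often readings are taken, Protocol 4.9 states: "Ulcer photographs and photographs of the index leg will be taken at each visit (Day 14 through Month 18". Protocol 4.11 states: "The VAS score must be documented at all visits". Table 3, however, marks VAS at six post-baseline visits, and the procedure lists for the 14-, 28- and 42-day visits omit it. Tracings are scheduled only at screening and Day 0.

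SAP 2.5.5 reworks the tables. For healing: "A table showing the number of subjects completely healed in the target ulcer will be provided at up to 6 months", followed by the periods beyond 6 to 12 and beyond 12 to 18 months. For size: "If available, the number of subjects with at least 20% reduction in bi-dimensional size (by measuring largest diameters) will be provided". For pain it tabulates the "number of subjects reduced by ≥ 20 mm from baseline in VAS score" in the same three periods. SAP 2.4.3 defines post-baseline clinic windows only at Months 3, 6, 9, 12, 15 and 18, uses one visit per window, and leaves out-of-window visits to the listings.

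The study is open-label and every subject is treated (SAP 2.2). Protocol 9.2 and SAP 2.4.1 call it unpowered and any testing descriptive.

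**The concern.** Under item 6 a subject is credited as soon as a counted reading falls below baseline, by however little. Because the count is cumulative, that credit is not withdrawn if the ulcer grows back. An ulcer that fluctuates around a fixed size therefore has a fresh chance of being counted at each reading, and the total can rise from Month 6 to Month 18 only because more readings are included. Item 7 has a threshold but shares the cumulative feature.

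With no control arm and no equal-sized worsening count beside it, nothing in the table shows how much of the count is fluctuation. A majority listed as improved would then say little about clinical benefit.

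**Working it through.** The documents give no expected improvement rate, null rate or measurement error, so there is no stated figure to reproduce. The rates below are conditional on the assumptions shown.

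**1. Item 6, any shrinkage.** Assume a constant true size and independent, equally distributed error at baseline and at k follow-up readings, without ties. The chance that baseline is the smallest of k+1 readings is 1/(k+1), so P(ever below baseline) = k/(k+1).

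| Readings that count | By Month 6 | By Month 12 | By Month 18 |
|---|---|---|---|
| Months 6, 12, 18 only | 1/2 = 50% | 2/3 = 67% | 3/4 = 75% |
| SAP windowed visits (2, 4, 6) | 2/3 = 67% | 4/5 = 80% | 6/7 = 86% |
| All photographed visits (8, 13, 18; Protocol Table 3) | 8/9 = 89% | 13/14 = 93% | 18/19 = 95% |

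If all 8–10 subjects had an ulcer, 75% would be 6.0 to 7.5 subjects. Rutherford 4 subjects need not have one, so the actual denominator may be smaller.

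**2. Sensitivity to the no-trend assumption** (simulation on log size, assumed CV).
- Untreated growth of 2% per month, CV 10–20%: 22–43% over three visits, 79–86% over 18.
- Untreated growth of 5% per month, CV 10–20%: 2–15% over three visits.
- Spontaneous shrinkage of 2% per month, CV 20%: 96% over three visits, 99.5% over 18.
- Ties: if shrinkage must reach an assumed 10% to be seen on a photograph, one visit gives 23–35% at CV 10–20% rather than 50%.

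**3. SAP thresholds, two readings per period.** The windows leave Months 3 and 6, then 9 and 12, then 15 and 18. Suppose either reading can qualify and there is no true change. With threshold c and reading SD σ, P = 1 − ∫ φ(z)[1 − Φ(z − c/σ)]² dz. For one reading this reduces to Φ(−c/(σ√2)).

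For ulcer size, c = −ln 0.8 = 0.223 and σ = √ln(1 + CV²). For VAS, c = 20 mm.

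| Measure, assumed error | One reading | Either of two |
|---|---|---|
| Ulcer, CV 15% | 14.5% | 24% |
| Ulcer, CV 20% | 21% | 33% |
| Ulcer, CV 25% | 26% | 39% |
| VAS, SD 10 mm | 8% | 13% |
| VAS, SD 15 mm | 17% | 28% |
| VAS, SD 20 mm | 24% | 37% |

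Over six VAS readings counted cumulatively, as item 7 allows, the figures are 27/47/59%.

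**4. What counts as equal worsening.** On the log scale a 20% reduction is mirrored by a factor of 1/0.8 = 1.25, a 25% increase. A 20% increase is not the mirror image: at CV 20% with no effect, 21% of subjects look at least 20% smaller but 26% look at least 20% larger.

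**The case against.** The strongest reply has four parts.

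- **Item 6 names Months 6, 12 and 18, not every visit.** This stands. A reader might infer from the visit-by-visit photographs that any visit qualifies. The protocol does not say so, and the 95% depends on that reading. The narrowest reading still gives 75% by Month 18 for stable ulcers.
- **An inert product does not imply a stable ulcer.** This also stands. A reader might take 50% as a floor and 95% as a ceiling, but the disease can progress, and Protocol 5.2 screens out ulcers that look set to heal unaided. Growth, ties, death or amputation can pull the share well below 50%, and spontaneous shrinkage can push it above 95%. Progression does not rescue the rule if all visits count, because ulcers growing 2% per month would still be counted as improved in 79–86% of cases.
- **The SAP has largely replaced item 6.** This is partly right. Its periods are disjoint, so the automatic rise over time does not carry into its tables, and its windows leave two readings per period rather than eight. But the size threshold applies only if data are available, the qualifying reading is undefined, and Protocol 9.1 is unchanged. VAS rates based on 18 visits should not be used, since only Protocol 4.11 supports that schedule.
- **Worsening is reported elsewhere and the study is descriptive.** SAP 2.5.5 plans a table of worsening index-leg events, VAS change by visit and Rutherford shifts. These help, but none is matched in size to the improvement counts. The objectives are feasibility, tolerability and safety, and nothing in the documents makes phase 3 depend on these counts. A reader might infer that such a decision rests on them, but the text does not support that.

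**Conclusion.** The concern holds in a limited form. As Protocol 9.1 item 6 is written, half of stable ulcers would be counted as improved at Month 6 and three quarters by Month 18 on the narrowest reading. This rests on no net trend, equal independent reading error and no ties.

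Under SAP 2.5.5, if any one windowed reading qualifies, about 24–39% false ulcer reductions and about 13/28/37% false VAS responses remain per period. The CVs and SDs behind those figures are assumed, since the documents give none.

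Rest pain shares the problem of repeated looks but not the missing threshold. The consequence is limited to how the benefit counts can be read. No test, error rate or primary objective is affected.

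**What to change.** Align Protocol 9.1 items 6 and 7 with SAP 2.5.5, including whether complete pain relief counts by itself, as it does in item 7 but not in the SAP table. Then:

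1. Keep confirmed complete healing as the only cumulative ulcer response, and remove mere shrinkage from that count.
2. Report ulcer size reduction of at least 20% and VAS reduction of at least 20 mm as status at the Month 6, 12 and 18 windowed visits, not at any reading in the period. Under no change this brings the false rates down to the one-reading column above.
3. Beside each, show the number worse by a matched amount: VAS at least 20 mm higher, and ulcer size at least 25% larger. Under the no-change model the paired counts have equal expectation, so a clear imbalance is informative. For VAS this assumes that few baselines lie so close to an end of the scale that a 20 mm move is impossible.

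The cost is revised wording and a few table columns from data already planned, with no added visits or readers. The downside is that the response counts become less favourable and transient improvement appears only in the listings.

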9.2. Statistical Methods

All summaries and analyses will be presented in tabular or graphical form. The study is not powered for the statistical inference and the test will be considered to be descriptive.

9.2.1. Disposition, Compliance, Demographic and Background Characteristics (Including Medical History)

The number subjects enrolled, and the number and percent of subjects who completed the study, prematurely discontinued, primary reason for discontinuation, and the compliance to the study product (number of subjects who received the first course of injections only, both the first and subsequent courses of injections) will be summarized.

The demographic data (age, weight, gender, race), and the prior and concomitant medication will be summarized at baseline and during the study. The use of selective concomitant medication such as medications for pain, hypertension, hyperlipidemia, antiplatelet agents will also be summarized.

9.2.2. Statistical Analysis for Efficacy and Safety

Categorical data will be summarized by the use of frequency tables showing the number and percentage of subjects falling within a particular category by visit, and detailed line listings of subjects will be provided.

Continuous data will be summarized by reporting number of observations, mean, standard deviation (SD), median, minimum and maximum by visit. Summary statistics will be provided for baseline and the change (with percent change) from baseline. A one-sample t-test will be performed on within group change-from-baseline for individual time point (Months 6, 9, 12, 15, and 18 with last observation data (assessed prior to intervention or worse score for deaths) carry-forward (LOCF)).

9.2.3. Windows for time points

Number of subjects followed up to 3 months: subjects with a follow-up visit at day 90 ± 10 (days 80 to 100) will be counted.

For months 6, 9, 12, 15 and 18 evaluation: subjects with follow-up visits at day $182 + 15$ (days 167 to 197), day $273 + 15$ (days 258 to 288), day $365 + 30$ (days 335 to 395), day $455 + 35$ (days 420 to 490), and day $548 + 45$ (days 503 to 593) will be counted.

For 12 months and 18 months evaluations, events occurring up to day 395 and day 593 will be taken into account, respectively.

10. SAFETY FOLLOW-UP PROGRAM

Since this study uses a DNA plasmid for gene transfer, the Sponsor (AnGes, Inc.) is complying with regulatory guidance to conduct long-term safety follow-up to collect safety information on all participants who receive the study product. The long-term safety follow-up data will be collected every 6 months for an additional 18 months following the Month 18 Visit.

Adverse Events should be documented and followed from the start of the first dose of study product (Day 0), until the final outcome is known or until the end of the study safety follow-up period. AEs (including SAEs) that have not resolved by the end of the study follow-up period should be recorded in the CRF as "ongoing". If it is not possible to obtain a final outcome for a SAE, the reason that a final outcome could not be obtained must be documented (e.g., completion of follow up, subject has moved and cannot be contacted, etc.). Serious Adverse Events should be reported within 24 hours of site awareness.

Deaths, major amputations, revascularizations by surgical bypass, stroke, and myocardial infarction will be source verified. An appropriate request/permission for this safety follow-up program will be included in the informed consent.

The data collected during the follow-up period will consist of surgical revascularization, lower limb amputation, cancers, eyesight changes, bleeding/blood disorders, autoimmune diseases, neurological disorders, hospitalizations, unexpected or significant illnesses including stroke, myocardial infarction, and death. In the event of death, information regarding the above data (as best as possible) and date and cause of death will be requested from a spouse or nearest relative. The questionnaire is found in Appendix F.

Site staff should obtain information from the completed questionnaires via phone contact within ± 7 days of the target follow-up contact date. If the subject has experienced any of the events types noted in the questionnaire additional information may need to be requested from the subject and/or supporting medical records may be required. In the event the subject experiences (CLI status of the index limb, revascularization of the index limb, amputation of the index limb, cancers, eyesight changes, bleeding/blood disorders, autoimmune diseases, neurological disorders, hospitalizations, and unexpected or significant illnesses including stroke, myocardial infarction, and death) data on relevant onset/resolution dates, treatments and confirmed diagnosis (as and where applicable) will be obtained.

All information collected by the questionnaire will be submitted periodically to the FDA and any other agencies as required.

All safety information collected by the questionnaire that is not included in the Biologics License Application (BLA) will be submitted periodically to the FDA and any other agencies as required. Subjects will not be identified in any report, publication, or submission. All subjects participating in the study will receive an explanation of these procedures, and their rights under HIPAA, at the time of Informed Consent.

11. ADMINISTRATIVE PROCEDURES

11.1. Institutional Review Board/ Ethics Committee

Regulatory Authorities require that an IRB/EC oversee all investigational drug studies (21 CFR 56). Each IRB/EC must conform to federal regulations and any country, state and local guidelines regarding such, will approve all aspects of the study, including but not limited to said protocol and written Informed Consent to be used, prior to initiation of the study. The Investigator will provide the Sponsor with a copy of the communication from the committee to the Investigator indicating approval of the protocol and consent form. All amendments to the protocol that affect the conduct of the study must be reviewed and approved prior to implementation, except where necessary to eliminate immediate hazards to human subjects.

As per IRB/EC requirements, the Investigator will be responsible for obtaining IRB/EC renewals; submitting expedited and other periodic safety reports to the IRB/EC for the duration of the study; and for following any additional reporting requirements by the IRB/EC approving study activity at his/her investigational site. Copies of all approvals, renewals and correspondence to and from the IRB/EC must be forwarded to the Sponsor.

11.2. Institutional Biosafety Committee (IBC)

The institution at which a gene transfer trial is being conducted shall establish an Institutional Biosafety Committee (IBC) whose responsibilities need not be restricted to recombinant DNA products. The IBC is responsible for conformance with the requirements set forth in the NIH Guidelines for Research Involving Recombinant DNA Molecules as defined in Section IV-B-2 for the US.

APPENDIX A. Study Product Preparation & Administration

1. SELECTION OF INJECTION SITE LOCATIONS

AMG0001 injection site locations will be identified using images from contrast arteriograms, CTA, or MRA and prior to Day 0. Injection sites will be determined by the independent vascular surgeon. Injection sites will be chosen with the objective of inducing the formation of bridging collaterals from areas with normal blood flow. Desirable locations for injections, above and/or below the knee, are areas of musculature proximal and distal to the occluded sites and areas adjacent to the occlusion where blood flow through collateral blood vessels is identified on the pre-procedure angiogram. Eight optimal injection site locations will be identified for all subjects prior to the planned Day 0. Injection sites will be indicated on an anatomical diagram prior to the planned Day 0.

- Subjects with no apparent occlusion above the knee will receive all 8 injections below the knee. Injections will be distributed between musculature adjacent to the Anterior Tibial Artery, the Posterior Tibial Artery, and the Peroneal Artery. Areas with good collateral flow should be considered ideal for injection site locations.
- When Subjects do have occlusions noted on the screening angiogram, the number of injections administered to each artery will be distributed in proportion to the severity of the occlusions at each location. Injections will be located in the proximity of the occlusion.

Desirable locations for injection are areas of musculature proximal and distal to the sites of vessel occlusion, in areas where there is good blood flow. Areas of ischemia should be avoided as sites for injection. The goal of duplex guided injection is to be certain that injection of the study product is placed into the muscle in proximity to the diseased vessel and not into the peri-vascular space.

It is advised that AMG0001 Injections not be administered into the gastrocnemius muscle due to the close proximity of major arterial anatomy. See Section 4.4 of this Appendix (below) for Injection Site Location examples.

